## 5.2 Treatment groups

Subjects will be analyzed in the following two treatment groups:

### Essure

- Subjects who initially attempted the Essure insertion procedure

### Laparoscopic tubal sterilization

- Subjects who initially attempted the laparoscopic tubal sterilization procedure

## 6 Statistical methodology

### 6.1 Population characteristics

#### 6.1.1 Background data

The numbers of subjects enrolled and included in the analysis populations will be tabulated by site. The reasons for subjects excluded from the analysis populations will also be tabulated.

The descriptive analysis will be performed for the baseline variables. All background data such as subject demographics, medical history, index event, risk factors, concomitant diseases and conditions as well as concomitant medication will be described by presenting frequencies and/or summary statistics. [Table 1](#) lists baseline variables to be presented for descriptive analysis. Tables on prior medication, concomitant medication will show frequencies using the WHO Drug Dictionary Version Q1 2016, or later if updated during the study, and the Anatomical Therapeutic Chemical (ATC) Classification codes.

**Table 1 - Baseline Variables**

	Endpoint/Variable
Demography	Age, ethnicity, race, employment status, occupation, hobbies, years of education, university/college degree, health insurance
Reproductive and Menstrual History	Age at menarche, number pregnancies, number ectopic pregnancies, number births, number vaginal births, number caesarean births, Time since last birth/abortion, miscarriage or live birth result in genetic abnormalities, absence of menstrual withdrawal bleeding during last 6 months, dysmenorrhea during last 6 months, intracyclic bleeding during last 6 months, unsuccessfully attempted to conceive, ever experienced premature labor, ever experienced premature delivery, ever experienced premature rupture of membranes, ever had dysmenorrhea, ever had pelvic pain not related to menses, ever had endometriosis, ever had dyspareunia, ever had adenomyosis, ever had fibroids, ever had pelvis inflammatory disease, ever had cone biopsy, ever had loop electrosurgical

	excision procedure, ever had sexually transmitted disease, ever had ovarian cyst, ever had breast cancer, ever had ovarian cancer, prescribed medication to control bleeding in last 2 years, prescribed medication to control lower abdominal pain in last 2 years,
Contraceptive Method at Baseline	Primary method used for contraception, duration of the contraceptive method used.
Abdominal/Pelvic Surgical History	Prior abdominal surgery (other than cesarean section), number of prior abdominal surgeries, time since most recent abdominal surgery, type of abdominal or pelvis surgery
Medical History	Type of medical history, dental history, history of depression, remarkable psychological history, victim of sexual abuse, positive family history of autoimmune disease, history of allergic/hypersensitive reactions, type of allergic/hypersensitive reactions, etiology of allergic/hypersensitive reactions, history of autoimmune like symptoms, type of autoimmune like symptoms, visited specialist, cosmetic permanent implants and/or piercings, medical implants, type of medical implants, dental and tattoo history, wear eyeglasses
Substance Use	Cigarette smoking status, cigarettes per day, duration of cigarette smoker, status of other tobacco habits, type of other habitual tobacco use, alcohol consumption status
Abdominal and Pelvic Exam	remarkable pelvic exam
Prior Medication	Type of medication, main indication for medication
Procedure Physician/Supervising Physician Characteristics	Have experience with Essure, number of Essure System placements in last month, last 12 months, total, successfully completed Essure System training, have experience with laparoscopic tubal sterilization, number of laparoscopic tubal sterilizations in last month, number of laparoscopic tubal sterilizations in last 12 months and total, physician specialty, years after graduating residency, facility/setting and percentages of physician who had a supervising physician for performing the sterilization

P-values for the differences between two groups will be given for flagging of baseline balance uncertainty. For continuous variables the t-test or Wilcoxon test will be used and for categorical variables the Chi-square test will be used.

### 6.1.2 Treatment characteristics

Characteristics describing the procedure will be tabulated by appropriate means.

### 6.1.3 Risk period definition

The safety outcomes analyzed are those occurring in the at-risk-period defined as the time from the index day (Day 0) until a specified censoring date as defined in Section 4.4. The censoring date is the earliest date of second sterilization method, hysterectomy surgery date, Essure removal date, or the date of hormonal manipulation start date for the primary analysis.

For some bleeding analyses the risk period will be restricted. For example, in the Essure group hormonal contraception is expected at least until the subjects are told to rely on Essure for permanent contraception. To have comparable risk periods in the two groups a similar restriction will be applied to the laparoscopic tubal sterilization group.

## 6.2 Adjudication

Adjudication will be discussed by the adjudication committee. Adverse events determined to constitute a validated outcome will be included in the analyses and those determined not to constitute a validated outcome will be excluded. There will also be a tabulation of the original assessment of events (prior to adjudication) considering the adjudicated, validated outcome.

## 6.3 Protocol deviations

Protocol deviations will be listed and summarized for all patients within the Full analysis set.

## 6.4 Outcome endpoints and variables

The main objective of this observational study is to evaluate under routine clinical practice conditions the incidence of important treatment-emergent AEs under hysteroscopic sterilization (Essure) and laparoscopic tubal sterilization. An AE is considered as treatment-emergent when it starts or worsens on or after the index date and up to the date of subject withdrawal or the censoring date, as described in Sections 4.3 and 6.1.3.

The outcome endpoint and variables are presented in Table 2. The descriptive analysis will be performed for all the variables listed below and the comparative analysis will be performed only for the main endpoints.

For the main endpoints, the subject incidence (regardless of the time each subject is “at risk”) is the number of subjects with treatment-emergent events divided by the number of subjects at risk.

Laboratory evaluation results will be compared to their normal ranges. Any values out of normal ranges will be identified. The change from baseline for each laboratory parameter will also be presented for each post-baseline visit.

**Table 2 - Outcome endpoints and variables collected during treatment**

	Endpoint/Variable
Main Endpoints	
 
Subjects reporting AEs of chronic lower abdominal and/or pelvic pain after sterilization procedure
 
Subjects reporting AEs of abnormal uterine bleeding after sterilization procedure
 
Subjects with reported allergic/hypersensitive reactions
 
Subjects with newly diagnosed autoimmune disorders
 

	Endpoint/Variable
	
 
Subjects undergoing invasive gynecologic surgery (e.g., device removal or hysterectomy) after sterilization procedure (excluding second Essure placement attempts)
 

Patient Reported Outcomes	
 
MOS SF-36 (Version 2) which includes eight distinct health domains (physical function, role-physical, bodily pain, mental health, role-emotional, social functioning, vitality, and general health perceptions) and physical component summary and mental component summary scores
 
PROMIS Scale V1.0—Pain Intensity 3a, raw score, T-Scores, percentages of subjects who had T-Scores more than 50 and 60
 
PROMIS Scale V1.0—Pain Interference 8a, raw score, T-Scores, percentages of subjects who had T-Scores more than 50 and 60
 
AMSS and two intermenstrual bleeding questions used to characterize bleeding in subjects undergoing Essure placement and laparoscopic tubal sterilization, total raw scores and individual score for each question, percentage of subject having total scores greater than 40
 
FSQ: to investigate if scores on this instrument (continuous and categorical) correlate with chronic pelvic pain over the course of the study
 
Supplemental PRO Questionnaires
 
Social Media Questionnaire
 

Additional Endpoints	
 
New exposure to metals including new cosmetic or medical permanent implants and/or piercings and its material, wear eyeglasses
 
Change from baseline to 1 Year in serum or plasma nickel level, titanium level— both categorical and continuous forms, association with adjudicated hypersensitivity/allergic/autoimmune events
 
Change from baseline to 1 Year in serum or plasma nickel level, titanium level association with adjudicated hypersensitivity/allergic/autoimmune events
 
Proportion of women who crossed over to alternate sterilization method (e.g., Essure subjects who attempted laparoscopic tubal sterilization)
 

Essure Insert Placement Procedure a	Type of hysteroscopy procedure, reason for second attempt, facility where procedure was performed, premedication, pregnancy test performed within 24 hours of this procedure, hormonal manipulation to promote atrophic or proliferate endometrium, anesthesia used, type of anesthesia used, placement technique, hysteroscopy possible, retroverted uterus, distention medium used, type of distention medium, duration of procedure, Essure procedure attempted, reason Essure procedure not attempted, experienced

	Endpoint/Variable
	AE during hysteroscopy, placement status (by tube), ostium in the field of vision during placement (by tube), if successful - number of Essure trailing coils, number of inserts used (by tube), device type, reasons for unsuccessful placement (by tube), primary reason for unsuccessful placement (by tube), first line confirmation test to be performed, investigator's rating of ease of use of the Essure device, physician's rating of procedure difficulty, experienced AE during Essure implant procedure, Primary method of contraception used just prior to procedure, Primary method of contraception used until reliance assessment, additional procedures performed in conjunction with the Essure procedure
Transvaginal Ultrasound a	Reason for TVU, facility where TVU performed, uterine position at time of TVU, insert detected (by tube), implant location (by tube), reason for unsatisfactory placement (by tube), TVU results satisfactory to allow the subject to rely on Essure, individual who performed TVU, individual who interpreted TVU, physician's rating of procedure difficulty, experienced AE during TVU
Hysterosalpingogram a	Timing of HSG, reason, HSG indication, TVU/HSG Algorithm requirement, type of difficult placement procedure, facility where HSG performed, uterine position at the time of HSG, insert detected (by tube), implant location (by tube), reason for unsatisfactory location (by tube), tubal occlusion (by tube), HSG results satisfactory to allow the subject to rely on Essure, individual who performed HSG, individual who interpreted HSG, experience AE during HSG
Essure Device Removal a	Physician Performing Procedure, Device removal intentional, reason for unintentional removal, primary reason for device removal, additional reasons for procedure, surgical method planned/performed, type of anesthesia, procedure related events, surgery result in permanent sterilization, procedures performed at time of device removal, reason why removal procedures were chosen, types of energy sources, vasoconstrictive agent used during removal, imaging procedures performed to localize inserts prior to removal, number of devices removed, location of device (per device removed), removal status (per device removed),
Reliance Assessment a	Timing of reliance assessment visit, imaging used for assessment, whether subject compliant and reason, subject instructed to rely on Essure inserts for contraception
Birth Control Counseling	Time of birth control counseling, reason for counseling on alternate method of birth control, method of birth control discussed with subject
Laparoscopic Tubal Sterilization b	Primary method of contraception used just prior to procedure, facility, pregnancy test performed within 24 hours of the procedure, type of procedure planned/performed, surgical method planned/performed, type of anesthesia, intraoperative findings, were both the specific procedure and surgical method completed as initially planned, complications during procedure, additional procedures performed, physician's assessment of

	Endpoint/Variable
	procedural difficulty, assessment of ability to access tubes, bilateral tubal occlusion achieved
Device Event	Any device event, type of device/problem, summary of device events, device event outcome, AE related to device event, device event evaluation
Adverse Events	Any AE, Serious AEs, reason for serious AE, AE of special safety interest, AE intensity, AE related to study procedures or devices, type of procedure/device related to AE, AE outcome, pre-existing condition, concomitant medication, other non-study procedures
Contraceptive Method Post-procedure	Method used for contraception, duration of the contraceptive method used.
Concomitant Medication	Type of medication, main indication for medication
Additional Abdominal or Pelvic Surgery	Type of surgery performed, was surgery done for the purpose of sterilization/ re-sterilization , surgery due to an AE
Allergy/Hypersensitivity Evaluation, Autoimmune Disorder Evaluation, and PRO Alert Response	Symptom subjects reported, adjudication committee form, pathological findings, serum or plasma nickel and titanium levels, NiLPT and chromium LPT results, cytokine samples analysis , type of alert, pain alert response and bleeding response.
Study Completion	Did subject complete study, primary reason for premature discontinuation, time to premature discontinuation
Death	Number subjects died

a Only measured for Essure Group

b Only measured for laparoscopic tubal sterilization group

For the main outcomes, [Table 3](#) lists the SMQ search terms for abnormal uterine bleeding and lower abdominal and/or pelvic pain. Per the definition by the American College of Obstetricians and Gynecologists, chronic pelvic pain is pain in the pelvic area that lasts for 6 months or longer (i.e., the stop date of the pain minus start date is longer than 182 days, or by the time of EOS, the subject still has pain ongoing with start date 182 days before EOS).

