28 JUN 2022

Version 5.0

Page: 9 of 149

	
Recruitment in the Essure arm is planned to continue as long as Essure is being implanted.
 
Enrollment in the laparoscopic tubal sterilization arm will be ceased once its enrollment reaches approximately 2:1 ratio laparoscopic tubal sterilization : Essure (anticipated).

Main variable(s)	
Section modified by Amendment 2 (Modification 7).
 
Pain: The proportion of subjects reporting AEs of chronic lower abdominal and / or pelvic pain after insertion of Essure System (ESS305) compared to the proportion of subjects reporting AEs of chronic lower abdominal and / or pelvic pain after laparoscopic tubal sterilization. Total incidence of pain events will be based on AE reporting.
 
Bleeding: The proportion of subjects reporting AEs of abnormal uterine bleeding after insertion of Essure System compared to the proportion of subjects reporting AEs of abnormal uterine bleeding after laparoscopic tubal sterilization. Total incidence of new onset or worsening abnormal bleeding events will be based on AE reporting.
 
Hypersensitivity / allergy: The proportion of subjects with adjudicated new onset or worsening allergic / hypersensitivity reactions (e.g., urticaria, rash, itching, as well as other symptoms that may be related to inflammation) in subjects wearing Essure inserts and in subjects undergoing laparoscopic tubal sterilization.
 
Autoimmune disorder: The proportion of subjects with adjudicated newly diagnosed or worsening autoimmune disorders in subjects wearing Essure inserts and in subjects undergoing laparoscopic tubal sterilization.
 
Proportion of subjects undergoing invasive gynecologic surgery after Essure placement (excluding second placement attempts); including Essure insert removal compared to the proportion of subjects undergoing invasive gynecologic surgery after laparoscopic tubal sterilization.

Time point / frame of measurement for primary variable(s)	
Section modified by Amendment 2 (Modification 17).
 
The main endpoints will be evaluated through 60 months of follow up after the procedure.

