In addition, any subject presenting with an AE of pelvic / lower abdominal pain and any subject presenting with symptoms she believes are due to hypersensitivity or allergic reaction will be evaluated per standard medical practice. In addition, this evaluation will include collection and submission of blood and serum samples to a central laboratory for a NiLPT, which is a measure of sensitization to nickel; a chromium LPT, which is a measure of sensitization to chromium; serum or plasma nickel level; and serum or plasma titanium level. If removal of a device or any other surgery is performed, pathological evaluation and metallurgic studies (if applicable) will be included. After the evaluation of the subject is complete, regardless of investigator's assessment as to whether or not a hypersensitivity / allergic reaction has occurred, all information will be forwarded to the adjudication committee (see Section 14.3) in a blinded fashion. If pathology / metallurgic studies are provided to the adjudication committee, it may not be possible to blind the members as to which group the subject belongs. Information forwarded to the adjudication committee will include all laboratory work for the subject, including baseline, 12 month (if applicable), and unscheduled draws. The final determination of whether or not a hypersensitivity / allergic event has occurred will be made by this committee.

- **Autoimmune disorders:** The proportion of subjects with adjudicated newly diagnosed or worsening autoimmune disorders in subjects wearing Essure inserts and in subjects undergoing laparoscopic tubal sterilization. Any subject presenting with symptoms indicating a potential autoimmune disorder will be evaluated per standard medical practice. All efforts will be made to obtain records of any diagnostic workup conducted by outside physicians. Blood samples for NiLPT, chromium LPT, serum or plasma nickel level, and serum or plasma titanium level will also be collected by the study site. An appropriate human leukocyte antigen (HLA) panel will be run on previously obtained baseline samples, if not already obtained at baseline. (The specific HLA type to be run will be dependent on the specific autoimmune disease the subject developed). If insufficient baseline sample exists, an additional sample may need to be drawn. After the evaluation of the subject is complete, regardless of investigator's assessment as to whether or not an autoimmune disorder exists, all

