6.2 Exclusion criteria

Section modified by Amendment 1 (Section 16.1) and Amendment 2 (Modification 10, Modification 11).

1. Subjects who are post-menopausal;
2. Subjects suspected of being or who are confirmed to be pregnant;
3. Subjects post-partum or having undergone pregnancy termination ≤ 6 weeks prior to scheduled procedure (Note: subjects may be screened and consented for the study prior to 6 weeks post-partum / post pregnancy termination; however, PRO tools must be administered > 6 weeks post-partum / pregnancy termination and the sterilization procedure must occur > 6 weeks post-partum / pregnancy termination);
4. Subjects uncertain about ending fertility;
5. Subjects with an active upper or lower genital tract infection;
6. Subjects with gynecologic malignancy (suspected or known);

7. Subjects who have had an attempted prior sterilization procedure (either laparoscopic or hysteroscopic);
8. Subjects scheduled to undergo concomitant intrauterine or laparoscopic procedures at the time of insert placement (intrauterine device removal/insertion is not considered a concomitant procedure) or laparoscopic sterilization;
9. Subjects with unexplained vaginal bleeding;
10. Any diseases or conditions that might interfere with the conduct of the study or the interpretation of the results (subjects with pre-existing conditions such as pelvic pain, autoimmune disease, or menorrhagia may be included at the discretion of the principal investigator);
11. Subjects who are direct employees or immediate family members of the Sponsor company or site investigators.

For the Essure group only:

12. Subjects who can have only one insert placed (including contralateral proximal tubal occlusion or suspected unicornuate uterus);
13. Subjects who have a known abnormal uterine cavity that makes visualization of the tubal ostia impossible and / or abnormal tubal anatomy or previous tubal ligation (including failed ligation);
14. Subjects who have had total or partial salpingectomies;
15. Subjects who are currently taking corticosteroids or immunosuppressive therapy;
16. Subjects with a known allergy to all contrast media available for use in HSG.

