10.3 Endpoints and planned statistical analyses

Section modified by Amendment 2 (Modification 3, Modification 25).

The following endpoints will be summarized as part of this study:

- The proportion of subjects reporting AEs of chronic lower abdominal and / or pelvic pain after insertion of Essure System compared to the proportion of subjects reporting AEs of chronic lower abdominal and / or pelvic pain after laparoscopic tubal sterilization. In both groups, AEs due to other apparent etiologies will be identified and excluded.
- The proportion of subjects reporting AEs of AUB after insertion of Essure System compared to the proportion of subjects reporting AEs of AUB after laparoscopic tubal sterilization. In both groups, AEs due to other apparent etiologies will be identified and excluded.
- Proportion of subjects with allergic / hypersensitivity reactions possibly attributed to wearing of Essure devices and allergic / hypersensitivity reactions in women undergoing laparoscopic tubal sterilization.
- Proportion of subjects with newly diagnosed autoimmune disorders in subjects wearing Essure inserts compared to subjects undergoing laparoscopic tubal sterilization.
- Proportion of subjects undergoing invasive gynecologic surgery after Essure placement (excluding second placement attempts), including Essure insert removal compared to the proportion of subjects undergoing gynecologic surgery after laparoscopic tubal sterilization.
- Patient reported outcome measures:
 - MOS SF-36 (Version 2);
 - PROMIS Scale V1.0—Pain Intensity 3a;
 - PROMIS Scale V1.0—Pain Interference 8a Participant Format;
 - AMSS and two intermenstrual bleeding questions used to characterize bleeding in subjects undergoing Essure placement and laparoscopic tubal sterilization;
 - FSQ: to investigate if scores on this instrument (continuous and categorical) correlate with chronic pelvic pain over the course of the study;
 - Supplemental PRO Questionnaires – a series of PRO tools used to actively solicit information on AEs commonly found in MDR reports with Essure;
 - Social Media Questionnaire – to elicit information about sources of influence on medical decisions, in particular, use of social media.

- Rates of AEs in subjects undergoing Essure placement and laparoscopic tubal sterilization;
- Characteristics of physicians performing the procedures;

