## **2 Study objectives**

The study has the following objectives:

- To evaluate the proportion of subjects who experience new onset or worsening chronic lower abdominal and / or pelvic pain who have undergone Essure placement (anyone who has had an attempt at placement defined as an insert that was placed in the operating channel of the hysteroscope will be included in the analysis, regardless of whether or not they are relying on Essure for contraception) compared to the proportion of subjects who had an attempt at laparoscopic tubal sterilization (defined as anyone who has had an incision or puncture of the skin, regardless of whether or not sterilization was successfully completed), and to better characterize these reported outcomes and identify pre-procedural and procedure-related characteristics that may be related to their occurrence.
- To evaluate the proportion of subjects who experience new onset or worsening abnormal uterine bleeding who have undergone Essure placement (as defined above) compared to the proportion of subjects who have undergone laparoscopic tubal sterilization (as defined above)

and to better characterize these reported outcomes and identify pre-procedural and procedure-related characteristics that may be related to their occurrence.

- To evaluate the proportion of subjects who undergo gynecologic or related surgical intervention (including “insert removal” and hysterectomy) after undergoing hysteroscopic sterilization with Essure versus laparoscopic tubal sterilization.
- To identify the proportion of subjects who experience new onset or worsening allergic, hypersensitivity, or autoimmune-like reactions after Essure placement or laparoscopic tubal sterilization and to better characterize these reported outcomes and any characteristics that may be related to their occurrence.
- To collect data on patient reported outcomes in subjects who have undergone hysteroscopic or laparoscopic tubal sterilization procedures.
- To collect rates of adverse events (AEs) in subjects undergoing Essure placement or laparoscopic tubal sterilization

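### The autoimmune main endpoint includes worsening in the protocol synopsis and 5.2.1 but only new diagnoses in SAP Table 2, SAP 7 and protocol 10.3 and 10.5, so flares in women with existing disease can fall outside the main comparison.

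*SAP*

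**What the plan says.** The documents define the autoimmune main endpoint in two ways.

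**Including worsening**
- Protocol synopsis, main variables: "The proportion of subjects with adjudicated newly diagnosed or worsening autoimmune disorders".
- Protocol 5.2.1: "adjudicated newly diagnosed or worsening autoimmune disorders".
- The objective, in the same words in protocol section 4 and SAP section 2, also points this way. It speaks of "new onset or worsening allergic, hypersensitivity, or autoimmune-like reactions".

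**New diagnoses only**
- SAP 6.4, Table 2, main endpoints: "Subjects with newly diagnosed autoimmune disorders".
- Protocol 10.3: "Proportion of subjects with newly diagnosed autoimmune disorders in subjects wearing Essure inserts".
- Protocol 10.5 and SAP 7 repeat the protocol 10.3 wording for the interim analyses.

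On eligibility, protocol 6.2 (criterion 10) says that "subjects with pre-existing conditions such as pelvic pain, autoimmune disease, or menorrhagia may be included" at the principal investigator's discretion. Pre-existing autoimmune disease is a candidate covariate for the propensity score in protocol 10.3 and SAP Table 5. Protocol 9.6.1.1 lists potential new or worsening autoimmune reactions as adverse events of special interest.

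**The concern.** Women who already have an autoimmune disease can be in both groups, and in them the safety question is whether the disease gets worse. Under the narrower wording they add to the denominator, but a flare of their known disease cannot enter the numerator.

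This matters because SAP 6.4 limits comparative analysis to the main endpoints. Risk differences by time interval (6.4.1), Kaplan-Meier estimates (6.4.3) and hazard ratios (6.4.4) are all specified for those endpoints. An event outside the endpoint definition is tabulated but not compared in that way. Neither document gives a reason for dropping worsening. The protocol also conflicts with itself, so following the protocol does not tell the analyst which count to produce.

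**Working it through.** The plan has no figure to reproduce here. Sample size follows the availability of Essure (protocol 10.4, SAP 4.1), and no event rate is stated for this endpoint. The check is mainly a reading of the text.

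**Step 1: which events each wording counts.** Take three women in the full analysis set.

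| Woman | Synopsis and 5.2.1 | Table 2, SAP 7, 10.3, 10.5 (literal) |
|---|---|---|
| No disease at baseline; new autoimmune diagnosis | Counted | Counted |
| Disease at baseline; a second, different autoimmune diagnosis | Counted | Counted |
| Disease at baseline; adjudicated worsening of that disease | Counted | Not counted |

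Only the third row differs. Nothing in SAP 6.1.3 or 6.4 removes this woman from the subjects at risk, so she stays in the denominator under both readings.

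**Step 2: whether other rules settle the third row.**
- SAP 6.4 calls an adverse event treatment-emergent if it starts or worsens on or after the index date, and uses such events in the main-endpoint numerator. This decides whether an event falls in the right period. It does not turn a flare of known disease into a new diagnosis.
- SAP 6.2 and 6.4 leave the final decision to the adjudication committee. Neither the SAP nor protocol 14.3 gives a rule for new versus worsening. Protocol 5.2.1 asks the committee whether a disorder has occurred, which does not say how a flare is coded.
- The sensitivity analysis in SAP 6.8 changes the censoring, not the endpoint definition.

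The third row can therefore be programmed either way.

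**Step 3: size, on assumed inputs.** The documents give neither the prevalence of existing disease (p) nor the probability of worsening over five years (w). The share of all women with an event that depends on the reading is p × w.

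| p (assumed) | w (assumed) | p × w |
|---|---|---|
| 2% | 10% | 0.02 × 0.10 = 0.2% |
| 2% | 50% | 0.02 × 0.50 = 1.0% |
| 8% | 10% | 0.08 × 0.10 = 0.8% |
| 8% | 50% | 0.08 × 0.50 = 4.0% |

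That is 2 to 40 women per 1,000. The only comparison the documents offer is the statement in protocol 9.6.1.1 that very few subjects are expected to develop an autoimmune disease.

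**The case against.** The strongest reply is that the Table 2 rows are short labels, not definitions. The allergy row omits adjudication, which SAP 6.4 nevertheless requires. The pain and bleeding rows omit new onset or worsening, although the objectives include both. On that view the starts-or-worsens rule and the committee's decision supply what the autoimmune row leaves out.

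Part of this stands: it shows that an analyst could reasonably include flares, so their omission is not certain. But the other rows are merely silent, whereas the autoimmune row carries a qualifier that excludes worsening. The same qualifier stands in the full endpoint statements of protocol 10.3 and 10.5 and SAP 7, which are not table labels.

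Three further objections are sound and limit the point.
- Flares are not lost to the study. They are adverse events of special interest and are tabulated under SAP 6.5.1, item 19.
- The objective concerns autoimmune-like reactions, a broader idea than diagnosed disorders. It supports including worsening but does not itself define this endpoint. The direct conflict is with the synopsis and 5.2.1.
- Women taking corticosteroids or immunosuppressive therapy are excluded from the Essure group only (protocol 6.2, criterion 15). The propensity score list has existing autoimmune disease but not its severity. A pooled total could therefore reflect a difference in case mix, which is a reason to report worsening separately as well.

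The analyses are exploratory, with no confirmatory test (SAP 4.2). That lowers the stakes but does not remove the need for one definition of a main endpoint.

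**Conclusion.** The inconsistency is in the current text and should be corrected. Read literally, SAP Table 2 leaves adjudicated worsening of existing autoimmune disease out of the main endpoint comparison. Read with the general rules of SAP 6.2 and 6.4, it might not. The affected share is about 0.2% to 4.0% of women, resting wholly on the assumed 2% to 8% prevalence and 10% to 50% worsening. Because few new cases are expected, even a handful of flares could change the comparison between groups.

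A reader might go further in two ways that the documents do not support. One is that about half of all events would be lost. That needs a rate of new diagnoses, such as 1% set beside 5% × 20% = 1.0% for flares, and the documents give none of these three figures. The other is that women with existing autoimmune disease are the most likely to react to a metal implant. Protocol 9.6.3.1 discusses nickel reactions in terms of sensitization and HLA type, not existing autoimmune disease.

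**What to change.** - **Definition.** In SAP Table 2, SAP 7 and protocol 10.3 and 10.5, word the endpoint as subjects with "adjudicated newly diagnosed or worsening autoimmune disorders", to match the synopsis and 5.2.1. If the narrower endpoint is intended, say so, give the reason, and change the synopsis and 5.2.1 to match.
- **Reporting.** Below the total, show newly diagnosed and worsening as two sub-rows. For worsening, use women with autoimmune disease at baseline as the denominator, since only they can worsen.
- **Adjudication output.** Record for each confirmed case whether it is a new disorder or a worsening of a known one.
- **Interpretation.** Note that the exclusion for corticosteroid or immunosuppressive therapy applies to the Essure group only, so the worsening sub-row may differ between groups for that reason.

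The cost is small: wording in four places and two table rows. Suspected and confirmed cases already go to the committee (protocol 14.3), and pre-existing condition is already a listed adverse event variable in SAP Table 2. The documents do not show whether the committee's form separates new from worsening. If it does not, one field must be added and completed for the cases already adjudicated. This should be done before database lock.
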